4.2.2.2. Population of interest

The primary pharmacodynamics analyses will be based on the Safety population and on participants who have completed the challenge visits (complete case analysis).

Statistical analyses

Unless otherwise specified, endpoints / variables defined in Section 4.2.1 will be summarised using descriptive statistics, graphically presented and listed (where appropriate).

Statistical Methodology Specification for Part 1

Endpoint / Variables	

 SP-induced wheal response-time AUC at challenge visit 1 	
Model Specification	

 Bayesian analysis of covariance (ANCOVA) 	
Model	$y_i \sim Normal(\mu_i, \sigma)$ $\mu_i = \mathbf{X}_i \boldsymbol{\beta}$
Response	y_i = AUC for participant i
Prior for σ	σ = between-participant SD $\sim Gamma$ (shape = 2, rate = $\frac{1}{A}$) with A reasonably large e.g. A=10 (Chung et al, 2013)
Population-level coefficients ($\boldsymbol{\beta}$)	$\boldsymbol{\beta}$ = parameters associated to predictors $\beta_k \sim Normal(0, sd = 1e6)$
Predictors (\mathbf{X})	
 SP = SP concentration (categorical) Saline-induced (Baseline) wheal response-time AUC (continuous)
Model Checking & Diagnostics	
See Section 4.1.1.1	
Model Results Presentation	

 Summaries of the posterior distributions of true AUC for each SP challenge and the true difference in AUC using the mean baseline to calculate the marginal estimates Probabilities that the true difference in AUC is greater than 0 	

Statistical Methodology Specification for Part 2

Endpoint / Variables	

 SP-induced wheal response-time AUC at challenge visits 1 and 2 (using only data when no IDM intervention was done) 	
Model Specification	

 Bayesian analysis of covariance (ANCOVA) with visit effects 	
Model	$\mathbf{Y} \sim MVN(\boldsymbol{\mu}, \boldsymbol{\Sigma})$ $\boldsymbol{\mu} = \mathbf{X}\boldsymbol{\beta} + \mathbf{Z}\boldsymbol{\gamma}$
Outcome	y_{ij} = SP-induced AUC for participant i at visit j

Prior for Σ (covariance matrix)	$\Sigma_{ij} = Cov[Y_i, Y_j]$ assumed to be unstructured $\Sigma \sim$ Inverse Wishart (J, R), with $J = 2$ (visits), R = empirical covariance matrix
Population-level coefficients (β)	β = parameters associated to predictors $\beta_k \sim Normal(0, sd = 1e6)$ β_0 = intercept, Vague: $Normal(0, sd = 1e6)$
Predictors (X)	
 SP = SP concentration (categorical) Visit = challenge visit (categorical) SP*visit = SP by-visit interactions (categorical) Saline_AUC_base = average baseline defined as the mean of the 2 saline-induced AUCs for each participant (continuous) Saline_AUC_visit = Deviation of each visit saline-induced baseline from average baseline defined as saline-induced AUC - Saline_AUC_base Saline_AUC_visit*visit = Saline_AUC_visit by-visit interactions
Subject-level effects (γ)	
 Z_i = design matrix for the subject-level effects $\gamma \sim Normal(0, \sigma^2 I)$
Model Checking & Diagnostics	
See Section 4.1.1.1	
Model Results Presentation	

 Summaries of the posterior distributions of true AUC for each SP challenge and the true difference in AUC using the mean baseline to calculate the marginal estimates Probabilities that the true difference in AUC is greater than 0 	

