**At each challenge visit, up to 4 concentrations of SP will be assessed, as follows:**

- In Parts 1 and 2:
  - Participants will first receive saline, by intradermal injection, and histamine by skin prick, as negative and positive controls.
  - If the wheal responses within the 20 min after each control challenge do not meet the acceptable saline and histamine responses (as defined in the SRM), the participant will not receive SP.
    - If it happens in Part 1 or on Challenge Visit 1 in Part 2, the participant will be withdrawn from the study.
    - If it happens on Challenge Visit 2 in Part 2 and if the participant marginally fails to meet the control criteria (as defined in the SRM), they may have the tests repeated. If they still fail to meet the control criteria, they will be withdrawn from the study.
  - Following confirmation of acceptable control responses, participants will receive up to 4 intradermal injections of SP at different concentrations; injections will be given sequentially from lowest to highest concentration; wheal and flare responses will be assessed after each challenge.

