4.1.1.1. Bayesian Inference

All the main statistical analyses will be carried out in the Bayesian framework. Models will be fitted by MCMC simulations. Vague priors will be used for modelling parameters and will be specified in the following sections. Sensitivity analyses on priors may be performed. Covariance structures may also be investigated..

The following summaries of the posterior distribution will be reported: posterior median, posterior standard deviation (SD), 95% equal-tailed credible interval (95% CrI), posterior probabilities of the true difference being greater than pre-specified thresholds.

The inference will be carried out as follows:

- 2 chains will be run, with different (over-dispersed) initial values in order to assess convergence. The posterior summaries will use only 1 chain.
- A minimum burn-in period of 10,000 MCMC samples (for each chain) will be used.

- A minimum of 10,000 MCMC samples (for each chain) will be run to generate samples of the posterior distribution.
- A thinning sample may be used to improve convergence. If k is the thinning ratio, the number of MCMC samples will be minimum $k*10,000$.

To assess convergence (MCMC), the following will be used:

- Ratio Monte Carlo error /posterior SD should be as small as to ensure that only a fraction of the posterior variability is due to simulation error.
The final MCMC samples will be such that this ratio for all the parameters in the model is ≤ 0.01 .
- Gelman & Rubin diagnostic is based on the ratio of the pooled variance across the chains over the overall within-chain variance. Values close to 1 indicate that each of the subsets of MCMC samples is close to the target posterior distribution.
A cut-off of 1.1 will be used.
- Diagnostic plots and visual inspection
 - o Trace plots (the distribution of points should not change as the chain progresses and the posterior mean and variance are relatively constant)
 - o Autocorrelation plots (provide information on how slow or fast the Markov chain converges)

To assess the model adequacy, diagnostic plots of the median predicted value vs median residual (should not show evidence of any patterns) will be used.

All the diagnostic outputs and alternative models fitted (where applicable) will be stored in the refdata folder in HARP (production) in the relevant reporting efforts.

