4.2.2. Main analytical approach

4.2.2.1. Summary Measure

The summary measure is the difference in wheal response AUC between 2 consecutive SP concentrations at challenge visit 1 (parts 1 and 2) and at challenge visit 2 (part 2).

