4.2.3. Sensitivity analyses

Sensitivity analyses on the priors (in particular the prior for the between-participant and within pa SD) will be carried out.

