4.3.2.3. Statistical Analyses

Endpoints / variables defined in Section 4.3.1 will be summarised using descriptive statistics, and graphically presented (where appropriate).

The proposed statistical analyses planned for the primary PD endpoint (Section 0) will be repeated for the flare response-time area under the curve (AUC) over the 2h post-challenge period for parts 1 and 2.

For the other endpoints, no statistical analyses will be carried out.

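### The Part 1 primary model has no participant term, so differences between consecutive SP concentrations within a participant are judged against the wrong variance

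*SAP*

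**What the plan says.** Protocol 4.1 states that, once the controls are acceptable, "participants will receive up to 4 intradermal injections of SP at different concentrations", in ascending order at one visit. SAP 4.2.2.1 sets the target: "The summary measure is the difference in wheal response AUC between 2 consecutive SP concentrations at challenge visit 1".

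For Part 1, SAP 4.2.2.2 specifies a Bayesian ANCOVA with a normal response, defined as "y_i = AUC for participant i". The predictors are concentration (categorical) and the participant's saline AUC (continuous). The only variance parameter is σ, labelled the between-participant SD, with a Gamma prior of shape 2 and rate 1/A, "with A reasonably large e.g. A=10". The outputs are posterior summaries of the AUC at each concentration and of the differences, plus the probability that each difference exceeds 0.

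The Part 2 table in the same section does include subject-level effects with their own distribution. SAP 4.2.3 promises sensitivity analyses on priors, "in particular the prior for the between-participant and within pa SD". SAP 4.1.1.1 adds that "Covariance structures may also be investigated". SAP 4.3.2.3 repeats the primary analysis for flare AUC. Protocol 9.4.2 names ANCOVA for Part 1, mentions random effects only for Part 2, and leaves room for alternatives.

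**The concern.** With one index, one SD and no participant effect, the Part 1 model treats a participant's AUCs as independent given concentration and saline AUC. Some people react more strongly than others at every concentration. Saline AUC is constant within a participant and removes only the part of that tendency that it explains linearly. The rest cancels from a within-participant difference, but the model leaves it in σ.

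The intervals and probabilities for consecutive differences are the Part 1 primary outputs. Protocol 2.2 gives poorly established variability as part of the background to the study, so a correct statement of uncertainty is one of its main products.

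**Working it through.** **Inputs.** Up to 4 SP AUCs per participant (Protocol 4.1); up to 12 participants in Part 1 (Protocol 9.2), so at most 12 × 4 = 48 rows. Neither the residual within-participant correlation ρ (after saline adjustment) nor the residual SD of AUC is in the documents; the ranges below are assumptions. The plan gives no precision figure to reproduce.

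**Formula.** Let σ_T be the total residual SD, equal at all concentrations, with n participants each having every concentration.

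- Model as written: Var(difference) = 2σ_T²/n.
- Actual: Var(difference) = (σ_T² + σ_T² − 2ρσ_T²)/n = 2σ_T²(1−ρ)/n.
- SE ratio = 1/√(1−ρ).

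If the estimated difference is 2 correct SEs above 0, the correct probability is Φ(2) = 0.977 and the model reports Φ(2√(1−ρ)).

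**Results with a vague σ prior.** The last three columns come from a simulation with 4,000 runs per cell, using the least-squares analogue of the model, in units of σ_T.

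| ρ | 1/√(1−ρ) | Φ(2√(1−ρ)) | Model SE / true SE, n=12 | Coverage of 95% interval, n=12 | Model SE / true SE, n=6 |
|---|---|---|---|---|---|
| 0 | 1.00 | 0.977 | 0.405/0.415 = 0.98 | 94.4% | 0.571/0.584 = 0.98 |
| 0.3 | 1.20 | 0.953 | 0.401/0.336 = 1.19 | 98.1% | 0.553/0.477 = 1.16 |
| 0.5 | 1.41 | 0.921 | 0.396/0.287 = 1.38 | 99.1% | 0.542/0.410 = 1.32 |
| 0.7 | 1.83 | 0.863 | 0.392/0.223 = 1.76 | 99.7% | 0.528/0.321 = 1.64 |

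With a within-participant error term, coverage at n=12 is 94% to 96% throughout. For a true step of 0.5 SD at n=12, the chance that the interval lies wholly above 0 rises from 19% to 30%, 17% to 40% and 13% to 59% at ρ = 0.3, 0.5 and 0.7.

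**Other quantities in the same model.** Intervals for the mean AUC at one concentration are little affected (coverage about 93% to 94% at n=12). The interval for the saline coefficient is too narrow: it covers 84%, 78% and 71% at ρ = 0.3, 0.5 and 0.7, because each participant is counted four times.

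**With the SAP's example prior.** Gamma(2, rate 1/10) has mean 2 × 10 = 20 and 99.9th percentile 92. If the residual SD is far above that, the prior pulls σ down: with 48 rows and residual SD 1000, the posterior mean of σ is about 643, against 1030 under a flat prior. A second simulation (12 × 4, 600 runs per cell) gives these median width ratios against a within-participant interval:

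| Prior and residual SD | ρ=0.3 | ρ=0.5 | ρ=0.7 |
|---|---|---|---|
| Flat, SD 1000 | 1.19 | 1.38 | 1.74 |
| Gamma, SD 20 | 1.16 | 1.34 | 1.72 |
| Gamma, SD 300 | 0.93 | 1.09 | 1.38 |
| Gamma, SD 1000 | 0.74 | 0.86 | 1.09 |

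Under the Gamma prior at SD 1000, coverage is 86%, 91% and 96% across these ρ values. At ρ = 0 it is already 80%, a shortfall due to the prior alone.

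**The case against.** Several points can be said for the plan.

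- **Flexible wording.** Alternatives and covariance structures may be explored. This is optional wording that specifies nothing for Part 1, so the stated primary model remains the one above.
- **Shorthand notation.** The Part 2 response also omits a concentration index, so the single index proves little. That is fair, but the omission also shows in the predictor, prior and variance rows, none of which has a participant component.
- **SAP 4.2.3 may mean Part 2.** The reference to a within-participant SD could be to that model. This stands; the section is supporting evidence only.
- **Limited harm.** With a vague prior and positive correlation the error for differences is conservative, no hypothesis is tested, and SAP Table 1 lists model-based analyses only for the Part 2 review. This stands and limits the consequence to the study report.
- **The prior is a separate matter.** A=10 is only an example, and prior sensitivity is planned. This is largely right, but the prior determines the net direction of the error and whether adding a participant term alone would be enough.
- **Idealised size.** The simple formula overstates the inflation somewhat in small samples, and Part 1 may stop at about 6 participants. If concentrations change between cohorts, some contrasts become partly between-participant. Their distortion is then smaller, but the estimates themselves can also differ with and without the term.

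**Conclusion.** The point holds: as written, the Part 1 primary model omits a participant term that its own summary measure requires. With a vague σ prior, equal variances and complete data, intervals for consecutive differences are too wide by 1/√(1−ρ), and the probability that a difference exceeds 0 is pulled towards 0.5. At ρ = 0 there is no error. Under the example prior the net direction depends on the AUC scale, which the documents do not settle. When every participant receives every concentration, the estimated differences are unaffected. The omission is certain; its size rests on the assumed ρ and SD. It should be fixed before analysis, but nothing in the documents shows that it drives the choice of concentrations.

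**What to change.** In SAP 4.2.2.2, index the Part 1 response by participant i and concentration k: y_ik ~ Normal(X_ik β + γ_i, σ_w), with γ_i ~ Normal(0, σ_b). Give σ_b and σ_w separate priors that are vague on the AUC scale, and state them. Adding the term while keeping A=10 could leave intervals too narrow if the SD is in the hundreds or thousands. Relabel the SDs as between-participant and within-participant, which also gives Part 1 the within-participant SD mentioned in SAP 4.2.3. Apply the same change to the Part 1 flare AUC model under SAP 4.3.2.3. The cost is a SAP wording change, one model term and one further prior; no new data are needed.

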### 2.2. Background

SP is a neuropeptide with an important role in neurogenic inflammation [Mashaghi, 2016]. When it is injected intradermally it causes wheal and flare responses, which increase in size with increased concentrations of SP [Borici-Mazi, 1999; Grouzmann, 2011; Sabroe, 1997; Zirbs, 2013]. While wheal and flare response to SP has been previously studied, the methods used to determine effect size differ between published reports and variability is difficult to establish. In addition, previous studies did not investigate possible modulation of pro-inflammatory markers and immune cells within the skin following SP challenge. This knowledge will aid the understanding of the mechanistic pathways downstream of SP activation.

Techniques such as intradermal microdialysis (IDM) can be used to take samples of interstitial fluid [Holmgaard, 2012; Baumann, 2019]. IDM involves insertion of dialysis membranes into the dermis, which is then perfused at a low speed with a physiological solution (the perfusate). Endogenous or exogenous molecules soluble in the extracellular fluid diffuse into the membrane and are collected in small vials for analysis. The technique has not previously been used to take samples from SP challenged skin.

This will be a 2-part study: Part 1 will aid understanding of the wheal and flare responses following intradermal SP Part 2 will investigate the variability of the responses, including the release of locally acting mediators and may include immune cells markers that can be detected in the skin after challenge..

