### 9.4.1. General Considerations

This is an exploratory enabling study which is primarily designed to define the relationship between SP concentrations and wheal and flare response, within a range of intradermal SP concentrations. There are no formal hypotheses to be tested.

All the statistical analyses will be carried out in the Bayesian framework. Models will be fitted by Markov chain Monte Carlo simulations. The following summaries of the posterior distribution will be reported: posterior mean, posterior standard deviation (SD), posterior median, 95% equal tailed credible interval, posterior probabilities of the true effect being greater than pre-specified thresholds. Vague prior distributions will be used.

For all endpoints, the baseline value will be the negative control value. No missing baseline will be allowed (as part of the inclusion/exclusion criteria).

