4.2. Primary Pharmacodynamic Analyses

4.2.1. Definition of endpoint

For parts 1 and 2, the primary endpoint is the wheal response-time area under the curve (AUC) over the 2h post-challenge period following skin challenge with ascending concentrations of SP on a single day (challenge visit 1) and 2 days (challenge visits 1 and 2), respectively, expressed as mm^2/min (see OPS).

The wheal response variable will be the area in millimetres squared (mm^2) and will be calculated using the following formula for area of an ellipse (see OPS), using the longest and orthogonal diameters measured by the calliper method.

The wheal response variable will be calculated for each ascending SP concentration and each control challenge (saline and histamine) and at each timepoint during the 2h post-challenge period at challenge visit 1 (parts 1 and 2) and challenge visit 2 (part 2).

The same as above will be repeated for flare.

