6.2.7. Handling of Missing data

Element	Reporting Detail
General	
 Missing data occurs when any requested data is not provided, leading to blank fields on the collection instrument: 
 These data will be indicated by the use of a ‘blank’ in participant listing displays. Unless all data for a specific visit are missing in which case the data is excluded from the table. Answers such as ‘Not applicable’ and ‘Not evaluable’ are not considered to be missing data and should be displayed as such.
Wheal and flare	
 No imputation methods will be used for missing value of the longest and orthogonal diameters
AUC	
 If there are single non-consecutive missing time points, or 2 consecutive missing time points, AUC will be calculated using trapezoidal rule (using non missing time points) If 3 or more consecutive time points are missing, AUC will be set to missing If 50% or more time points are missing, AUC will be set to missing If at least 50% points are non-missing, and the last 2 timepoints are missing, the AUC will be calculated using non-missing timepoints up to N-2
Biomarkers (IDM)	
 No imputation methods will be used for missing value.
AE	
 A worst-case scenario approach will be taken to handle missing data: if the relationship to study intervention is missing, the relationship will be “yes”, if severity is missing the severity will be set to ‘severe’, if seriousness is missing the seriousness will be set to ‘yes’

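### The only value given for the Part 1 prior on sigma, A=10, is not tied to the AUC scale; if the AUC is in mm²·min with an SD above about 120, it is not the vague prior promised

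*SAP*

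**What the plan says.** The Part 1 model (SAP 4.2.2.2) is a Bayesian ANCOVA with concentration as a factor and the saline AUC as a covariate. The response is defined as "y_i = AUC for participant i", and no participant term is listed. The SD has a Gamma(shape 2, rate 1/A) prior, "with A reasonably large e.g. A=10"; no other value of A appears. The regression coefficients have normal priors with SD 1e6.

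Both documents commit to weak priors. Protocol 9.4.1 states "Vague prior distributions will be used". SAP 4.1.1.1 states "Vague priors will be used for modelling parameters and will be specified in the following sections".

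On the scale of the outcome, SAP 4.2.1 has the AUC "expressed as mm^2/min (see OPS" (the programming specification is not among the documents). SAP 6.2.7 says, for series with a few missing points, "AUC will be calculated using trapezoidal rule (using non missing time points"; no division by time is mentioned. Neither document gives a wheal size, an AUC or an SD, and Protocol 2.2 says of earlier work that "variability is difficult to establish".

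The summary measure is the difference in AUC between consecutive concentrations (SAP 4.2.2.1). SAP 4.2.3 plans sensitivity analyses on the SD priors. SAP 4.3.2.3 applies the same model to flare AUC.

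**The concern.** Whether 10 is large depends on the unit of the outcome. Areas in mm² integrated over 120 minutes give mm²·min, and on that scale an SD of 120 is only 1 mm² averaged over the two hours (120/120). A prior with almost no mass above 92 could then pull sigma down, in a model whose priors are meant to be vague. The coefficient priors, at 1e6, could not have this effect; only the SD prior could.

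What is at stake is the set of Part 1 model results for the primary endpoint: the credible intervals for AUC at each concentration, the intervals for differences, and P(difference > 0), for wheal and then for flare.

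**Working it through.** **Inputs from the documents.** Up to 12 participants in Part 1 and up to 4 concentrations each, so 48 AUCs. There are 5 coefficients (4 concentrations, 1 covariate), so residual df = 48 − 5 = 43. Intervals are 95% equal-tailed. The documents give no figure for the SD or for interval width to reproduce.

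**Assumed.** The SD of the AUC (range shown), and the correlation ρ among a participant's AUCs (0 to 0.7).

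**1. The prior.** Gamma(2, rate 1/10) has mean 20, median 16.8, 95th percentile 47.4, 99th percentile 66.4 and 99.9th percentile 92.3. P(sigma > 120) = 0.00008.

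**2. Interval width.** With flat coefficients, the posterior of sigma is proportional to sigma^−43 × exp(−43 s²/(2 sigma²)) × prior. The prior is sigma × exp(−sigma/A) for the SAP, or 1/sigma for the reference, which gives the usual t interval. The table shows the width with A=10 divided by the reference width.

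| SD | 20 | 50 | 100 | 123 | 300 | 1000 |
|---|---|---|---|---|---|---|
| n=12 | 1.00 | 0.965 | 0.92 | 0.90 | 0.80 | 0.63 |
| n=6 | 0.99 | 0.92 | 0.84 | 0.81 | 0.675 | 0.495 |

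At n=12 the width falls 5% below reference at SD 64 and 10% below at SD 123. At n=6 (24 − 5 = 19 df) the corresponding SDs are 36 and 60. The n=6 row applies only if Part 1 stops at about 6 participants, which SAP 4.7 allows. If only the concentrations change, all participants still inform the single sigma.

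**3. P(difference > 0).** A reference value of 0.90 becomes 0.91, 0.92, 0.94 and 0.98 at SD 50, 100, 300 and 1000 (n=12).

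**4. Coverage at n=12, A=10, model as written.** The within-participant sum of squares is SD²(1−ρ) times chi-square(33). The between-participant sum is SD²(1+3ρ) times chi-square(10). Their total divided by 43 gives s², and h(s) is the half-width per unit standard error. A mean is covered with probability 2Φ(h/SD) − 1. A difference is covered with probability 2Φ(h/(SD√(1−ρ))) − 1, because the model uses variance 2sigma²/12 where the true variance is 2SD²(1−ρ)/12.

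| SD | Means, ρ = 0 to 0.7 | Differences, ρ = 0 / 0.3 / 0.5 / 0.7 |
|---|---|---|
| 50 | 94-93% | 94 / 97 / 99 / 99.8% |
| 123 | 92-91% | 92 / 96 / 98 / 99.6% |
| 300 | 89-87% | 89 / 94 / 97 / 99% |
| 1000 | 79-77% | 79 / 86 / 91 / 97% |

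**5. Is an SD of 123 plausible?** This can only be illustrated. Assume a wheal with a plateau from 10 to 20 minutes that declines to zero at 60 or 120 minutes. Peak diameters of 3, 5 and 10 mm then give AUCs of 247-459, 687-1276 and 2749-5105 mm²·min. An SD of 123 is a coefficient of variation of 27-50%, 10-18% and 2-4% respectively. Small wheals with low variability would be barely affected; larger wheals would be.

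**6. Time-averaged AUC.** With an SD of about 5 to 20 mm² (assumption), the width ratio at n=12 is 1.00-1.02, so the prior is harmless.

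**7. Larger A.** The ratio depends only on SD/A. At SD/A of 1, 2, 5, 10 and 30 it is 1.01, 1.00, 0.965, 0.92 and 0.80 (n=12). With A=1000 it is 1.00-1.03 for SD 20 to 2000.

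**The case against.** A=10 is an example. The instruction is that A be reasonably large, so an analyst who chose 1000 would comply, and the documents do not contradict their own vague-prior commitment. That stands. The gap is an unfixed hyperparameter whose only example may be poor on the likely scale.

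A reader might infer that Part 1 intervals are generally too narrow. The documents do not support that. The summary measure is a difference within participants, and the model ignores the pairing, which widens those intervals. At SD 123 the difference intervals already over-cover once the correlation is 0.3 or more.

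A reader might also infer that the choice of concentrations is affected. Table 1 of SAP 4.7 lists plots and, at the third review, summary tables for Part 1; model results are listed only for the Part 2 review. No hypothesis is tested, and no threshold on P(difference > 0) drives a decision.

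Nor does the point extend to Part 2. That model has a "design matrix for the subject-level effects" and normally distributed subject effects, but no prior is stated for their SD, so nothing says this Gamma prior applies there.

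The planned sensitivity analysis concerns exactly this parameter and would probably reveal an influential A. But it lists no alternative values and does not settle the primary prior.

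**Conclusion.** The point holds in conditional form and is minor. It rests on two assumptions that the documents cannot confirm: that the AUC is in mm²·min, and that its SD exceeds about 120. Under both, A=10 is informative. At n=12, intervals are at least 10% narrower than reference within the same model, and intervals for per-concentration means fall short of 95%. For consecutive differences the direction of the net error depends on the SD and the within-participant correlation. With an SD of 50 or less, or a time-averaged AUC, little changes at n=12.

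**What to change.** 1. Confirm the AUC unit against the programming specification and correct the label in SAP 4.2.1 if needed.
2. Before analysis, fix A on that scale, separately for wheal and flare, at no less than half the largest plausible SD (width ratio 1.00 at n=12 and 0.99 at n=6 when SD/A = 2). For wheal in mm²·min, A=1000 would serve for SDs up to 2000. Set the flare value from a stated flare-scale assumption. Rescaling the AUC by a pre-specified constant is an alternative.
3. Add a participant effect to the Part 1 model in the same change. A=1000 alone gives differences 98-99.9% coverage at correlation 0.3-0.7. A participant effect alone, with A=10 on both SDs and SD 300, gives differences 88-93% and means 82-87%. Together, at SD 300-1000 and n=12, differences are at 94-97% and means at 96-97%. The participant-effect figures come from one simulation of 2000 datasets per scenario and are approximate.
4. Name A=10 and the other values to be run under SAP 4.2.3.
5. State the prior for the Part 2 subject-level SD.

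The cost is a unit check and a few lines in the model tables. With A=1000, intervals are up to about 3% wider than reference at n=12 and 7% at n=6. If Part 1 stops at about 6 participants, the same simulation suggests that mean intervals become conservative with the participant effect (98-99.7%), because few participants inform its SD.
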